7.2. Administration of Investigational Medicinal Product

Patients will be instructed to ingest, placebo study drug starting at Visit S2 for the duration the placebo run-in period and the IMP starting at Visit T1 for the duration of treatment period orally once daily (once every 24 hours) at approximately the same time each day with water. IMP may be taken with or without food. On clinic visit days, patients will be instructed to delay ingestion of IMP until all study procedures have been completed.

If the patient fails to take IMP, details describing the reasons for nondosing should be documented in the patient's medical records and eCRF. Extra IMP (7 extra days per bottle) is provided and can be used, if needed, prior to the next visit or to replace a dose of IMP that cannot be used because it is lost or damaged.

Table 1: Investigational Product

	Investigational Medicinal Product	
Product Name:	Bempedoic acid	Placebo
Dosage Form:	Film-coated tablets	Film-coated tablets
Unit Dose:	180 mg	Not applicable
Container/Closure^a:	100-count bottle with screw on, child-proof cap	35- or 100-count bottle (depending upon visit) with screw on, child-proof cap
Route of Administration:	Oral, once per day, with or without food	Oral, once per day, with or without food
Physical Description:		

^a A 100-day supply of study drug will be included in the 100-count bottle and a 35-day supply of single blind placebo will be included in the 35-count bottle.

7.3. Concomitant Medications

Patients will be questioned about their concomitant medication use at each clinic visit. All concomitant medication taken chronically or intermittently during the study must be recorded with indication, total daily dose, and start and stop dates of administration.

The Prior/Concomitant electronic case report form (eCRF) will be used to record medications, herbal remedies, vitamins, other supplements, and over-the-counter medications taken within 3 months prior to screening (Week -5 Visit S1) and during the study.

7.3.1. Lipid-Regulating Medications and Supplements

Patients are allowed to continue their background lipid-lowering therapy during this study as long as the drugs and doses are stable for 4 weeks prior to screening (at least 3 doses are required for PCSK9 inhibitors). Use of fibrates must be stable at least 6 weeks prior to screening (Week -5 Visit S1). Stable lipid-modifying therapy(s) includes, but is not limited to, monotherapies or combination therapies and include:

Statins

Patients currently tolerating very-low-dose statin therapy are also considered to be statin intolerant and may continue taking that statin/dose throughout the study provided that it is stable (used for at least 4 weeks prior to screening) and well tolerated.

Average daily dose:

- rosuvastatin <5 mg,
- atorvastatin <10 mg,
- simvastatin <10 mg,

- lovastatin <20 mg,
- pravastatin <40 mg,
- fluvastatin <40 mg, or
- pitavastatin <2 mg)

Selective cholesterol and/or bile acid absorption inhibitors

- Cholestyramine/Colestyramine (Questran[®], Questran Light[®], Prevalite[®], Locholest[®], Locholest[®] Light)
- Colestipol (Colestid[®])
- Colesevelam hydrochloride (Welchol[®], Cholestagel[®])
- Ezetimibe (Zetia[®], Ezetrol[®])

Fibrates

- Fenofibrate (Antara[®], Lofibra[®], Tricor[®], Triglide[™], Lipantil[®], Supralip[®])*
- Bezafibrate (Bezalip[®])
- Ciprofibrate (Modalim[®])

* Note that gemfibrozil (lopilid[®]) is exclusionary in patients taking a very low dose statin as per co-administration prescribing instructions.

PCSK9 inhibitors

- Alirocumab (Praluent[®])
- Evolocumab (Repatha[®])

Other

- Niacin (Niaspan[®], Niacor[®], Slo-Niacin[®])
- Combination statin products must be at or below the above listed average daily statin dose.

7.3.2. Prohibited Medications

The use of the following medications and/or supplements are prohibited during the study.

- Statins at average daily doses of rosuvastatin ≥ 5 mg, atorvastatin ≥ 10 mg, simvastatin ≥ 10 mg, lovastatin ≥ 20 mg, pravastatin ≥ 40 mg, fluvastatin ≥ 40 mg, or pitavastatin ≥ 2 mg
- New or planned dose changes of systemic corticosteroids.
Note: Stable doses of systemic corticosteroids at screening are allowed (≥ 4 weeks from Visit S1). Topical and inhaled steroids are allowed.
- Red yeast rice (monacolin K) extract and Berberine-containing products must be discontinued 2 weeks prior to screening (Week -5, Visit S1).

- Lomitapide or apheresis therapy within 3 months to screening (Week -5, Visit S1).
- Mipomersen within 6 months to screening (Week -5, Visit S1).
- CETP-I within the last 2 years to screening (Week -5, Visit S1) except for Evaceptapib within the last 3 months to screening (Week -5, Visit S1).
- New or planned anti-arrhythmia medication(s) within 3 months to screening (Week -5, Visit S1).
- Previous enrollment into a study of an experimental siRNA of PCSK9 or use of any other experimental or investigational drugs within 30 days to screening (Week -5, Visit S1).
- Gemfibrozil in patients taking a very low dose statin as per co-administration prescribing instructions.

7.3.3. Allowable Medications

Patients must be on stable concomitant medication regimen(s) for the following medications and/or supplements:

- Hormone replacement therapy within 6 weeks of randomization
- Thyroid replacement therapy within 6 weeks of randomization. Diabetic medication(s) within 4 weeks of randomization.
- Obesity medication(s) within 4 weeks of randomization.
- Oral lipid-modifying therapy within 4 weeks to screening (Week -5, Visit S1).
- PCSK9 inhibitors (alirocumab or evolocumab) if at least 3 doses prior to Visit S1. Patients who were previously (either investigational or commercial) on a PCSK9 inhibitor, must have discontinued 4 months prior to screening (Week -5, Visit S1)
- Hypertensive medication(s) within 2 weeks prior to randomization.
- Hypertriglyceridemia medication(s) within 4 weeks prior to screening (Week -5, Visit S1) with the exception of fibrates that are within 6 weeks prior to screening (Week -5, Visit S1)

7.4. Patient Lifestyle and Dietary Guidelines

Patients will be counseled to follow a lipid-lowering diet as per local or regional guidelines and should be encouraged (as able) to participate in a regular exercise program throughout the study.

7.5. Treatment Compliance

Screening Compliance

No study medication treatment will be given during the Screening period; therefore, compliance will not be assessed.

Placebo Run-In Adherence to Study Medication

At visits Week -1 (S3) and Week 0 (T1), designated clinical site staff will assess patient study drug compliance by counting the number of tablets that are returned as unused and by querying the patient with regards to daily intake. If at the Week -1 (S3) visit the patient has not taken all doses of study drug(s) as instructed, the patient will be queried for a reason, findings will be documented, and the patient will be counseled on the importance of carefully following all dosing instructions. Factors contributing to poor adherence will be determined and, if possible, remedied. If at the T1 visit, the average study drug compliance from the placebo run-in period is <80%, or if the patient experiences an adverse event related to the run-in single blind placebo, the patient will not go onto randomization.

Treatment Period Adherence to Study Medication and Procedures

At each patient visit during the treatment period, designated clinical site staff will assess patient study drug compliance by counting the number of tablets that are returned as unused and by querying the patient with regards to daily intake. If the patient has not taken all doses of study drug(s) as instructed, the patient will be queried for a reason, findings will be documented, and the patient will be counseled on the importance of carefully following all dosing instructions. Factors contributing to poor adherence will be determined and, if possible, remedied. Patients demonstrating poor adherence will continue to be counseled on the importance of carefully following all dosing instructions, but will not be removed from the study.

8. STUDY PROCEDURES AND SCHEDULE OF ASSESSMENTS

8.1. Informed Consent

The patient must be adequately informed of the nature and risks of the study and understand the informed consent document (ICD). No study-related procedure will be performed until the patient has been completely informed of the study, has freely consented to take part in the study, and has signed and dated an ICD approved by the Sponsor (or designee) and the Institutional Review Board (IRB) or Independent Ethics Committee (IEC).

8.2. Confirmation of Statin Intolerance (SI)

The investigator is responsible for reviewing the patient's available medical records and assessing the patient for SI. This will include a review of statin use history.

Both the patient and the investigator will sign a form confirming that that the patient is statin intolerant. Within this form, the patient will acknowledge an understanding that they are at high risk for experiencing a heart attack or stroke and death and that using a statin would reduce that risk; however, they are not taking a statin because of intolerable side effects that started or increased during statin therapy and resolved or improved when statin therapy was discontinued. Within the same form, the investigator will confirm that the patient is unable to tolerate statin therapy (except possibly at very low average daily doses of atorvastatin <10 mg, fluvastatin <40 mg, lovastatin <20 mg, pravastatin <40 mg, pitavastatin <2 mg, rosuvastatin <5 mg, or simvastatin <10 mg) based on review of the medical history and discussion with the patient.

Documentation of prior statin use will be based on patient recall and copies of relevant medical records and pharmacy records if readily available. If investigator is unable to assess prior statin use due to poor patient recall and/or lack of relevant medical records, and if appropriate according to local medical practice, documentation of contact with primary care physician regarding prior statin use should be obtained. At minimum, there will need to be documentation for the name of 2 statins and the dose of at least 1 statin attempted at low dose to ensure inclusion criteria is met. All available prior statin use history will be recorded in the eCRF. Additionally, the basis for the investigator's confirmation of the patient's SI will be noted in the eCRF.

8.3. Procedures and Schedule of Assessments

The study will be conducted as outlined in the following sections. [Table 2](#) summarizes the study assessments at each study visit for patients enrolled in this study, followed by an overview of assessments by visit in [Sections 8.3.1-8.3.8](#). Further details of the assessments are provided in the Study Operations Manual.

Table 2: Schedule of Events (Subject Visit Schedule)

Visit	S1 ^{1,2}	S2	S3	T1	T2	T3/phone	T4	T5/EOS ³
Week	Wk -5	Wk -4	Wk -1	Wk 0	Wk 4	Wk 8	Wk 12	Wk 24
Procedure	Day -63 to -29	Day -28 ±3	Day -7±3	Day 1	Day 29±3	Day 57±3	Day 85±3	Day 169 ±7
Informed Consent	X							
Enrollment Criteria	X							
Demographics	X							
Medical History	X							
Statin Intolerance Status Determination	X							
Concomitant Medications	X	X	X	X	X	X	X	X
Adverse Event Recording		X	X	X	X	X	X	X
Physical Exam		X						X
Weight ⁴	X			X			X	X
Height/BMI	X							
12-Lead ECG ⁵			X					X
Vital Signs ⁶	X	X	X	X	X		X	X
Serology ⁷	X							
Serum Pregnancy ⁸	X							
Urine Pregnancy ⁹				X				
TSH	X							
Clinical Safety Labs ¹⁰	X		X	X	X		X	X
Basic Fasting Lipids ¹¹	X		X	X	X		X	X

Table 2: Schedule of Events (Subject Visit Schedule)

Visit	S1 ^{1,2}	S2	S3	T1	T2	T3/phone	T4	T5/EOS ³
Week	Wk -5	Wk -4	Wk -1	Wk 0	Wk 4	Wk 8	Wk 12	Wk 24
Procedure	Day -63 to -29	Day -28 ±3	Day -7±3	Day 1	Day 29±3	Day 57±3	Day 85±3	Day 169 ±7
HbA _{1c}	X			X			X	X
PK sample					X		X	X
apoB				X			X	X
hs-CRP				X			X	X
Diet and exercise counseling ¹²	X	X	X	X	X	X	X	
Establish Patient Eligibility		X		X				
Randomization				X				
IWRS Contact ¹³	X	X		X			X	X
Single-blind Drug Dispensing		X						
Double-blind Drug Dispensing				X			X	
Drug Return/Compliance			X	X	X		X	X

NOTE: For patients who withdraw from study drug treatment, but consent to be followed for safety assessments and return to clinic for these visits, the visits will occur according to the protocol schedule. Safety assessments should include clinical safety and basic lipid laboratories (except for apoB and hs-CRP), adverse events (AEs), physical examination (PE), vital signs, and electrocardiograms (ECGs).

¹ An optional fasting (minimum of 10 hours) TG assessment MAY be completed between Visits S1 and S2 (prior to starting single-blind medication) if patient fails to meet TG criterion at Visit S1. The repeat value will be used to determine eligibility.

² A recheck of blood pressure may be completed between Visits S1 and S2 if the patient's DBP and/or SBP meet the exclusion criteria levels. Patients may randomize after blood pressure medications have been adjusted, the patients have been on stable doses of blood pressure medications for at least 2 weeks, and the repeat blood pressure values (diastolic blood pressure [DBP] and/or systolic blood pressure [SBP]) do not meet exclusionary values. Repeat labs may be completed between Visit S1 and Visit S2 to determine eligibility if the patient's estimated glomerular filtration rate (eGFR), alanine aminotransferase (ALT), aspartate aminotransferase (AST) or other labs meet exclusion criteria levels. If this optional lab is completed, the repeated value will be used to determine eligibility.

³ All procedures will be completed for all patients at either EOS if completing the study or early withdrawal.

⁴ Body weight will be measured while fasting, using consistent scales, after voiding, and without shoes and outerwear (eg, coats).

⁵ Single 12-lead ECG will be performed prior to any blood sample collection.

⁶ Vital signs will include DBP, SBP, heart rate (HR) and will be collected prior to any blood sample collection. Patient will rest for 5 minutes prior to assessments.

⁷ Serology for HbsAg, HCV-ABVivi.

⁸ Pregnancy test completed in women of child-bearing potential only. FSH in naturally postmenopausal women ≥ 1 year without menses and < 55 years;

⁹ Urine pregnancy test completed in women of child-bearing potential only just prior to randomization.

¹⁰ Clinical safety labs include hematology, blood chemistry, and urinalysis at all visits. A coagulation panel will be completed for all patients at Week -5 (Visit S1). A coagulation panel will be completed only for patients on vitamin K antagonists at Day 1 (Visit T1) and 3 to 5 days later. For these visits, the sample may be analyzed at either the central or a local lab. Please refer to laboratory manual for detailed schedule of tests.

¹¹ Basic fasting (minimum of 10 hours) lipids include total cholesterol, calculated low-density lipoprotein cholesterol (LDL-C), high-density lipoprotein cholesterol (HDL-C), non-HDL-C, and triglycerides.

¹² Diet and exercise counseling per local and/or regional guidelines for the management of hyperlipidemia.

¹³ Interactive web response system (IWRS) contact at either an early withdrawal or an EOS visit to register study discontinuation visit date.

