In this hierarchical testing structure, each hypothesis is tested at a significance level of 0.05, two-sided. Statistical significance at each step is required in order to test the next hypothesis. If the primary endpoint meets the criteria for statistical significance, then the percent change from baseline to Week 24 in LDL-C will be tested; and so forth.

For the remaining secondary efficacy endpoints and the tertiary efficacy endpoints, a significance level of 0.05 will be used; given the large number of remaining endpoints, the p-values for those endpoints will be considered descriptive.

Percent change from baseline to Week 24 in LDL-C; change from baseline to Weeks 12 and 24 in LDL-C; percent change from baseline to Weeks 12 [REDACTED] in [REDACTED] non-HDL-C, [REDACTED] TC, apoB, and

hs-CRP will each be analyzed using ANCOVA with treatment group and patient type (primary prevention; secondary prevention) as factors and the relevant baseline as a covariate. Baseline for [REDACTED] non-HDL-C, [REDACTED] and TC will be defined as the mean of the lipid values from Week -1 (Visit S3) and predose Day 1/Week 0 (Visit T1). Baseline for apoB and hs-CRP will be defined as the predose Day 1/Week 0 (Visit T1) value. Each ANCOVA will be performed using the FAS, with patients included in their randomized treatment group regardless of the treatment they actually received. Only observed case data will be included in each analysis (no imputation will be performed for missing data). For each lipid parameter and analysis time point, the LSM and SE will be provided for both treatment groups, along with the placebo-corrected LSM, its 95% CI and associated p-value.

For all continuous efficacy endpoints (percent change from baseline in LDL-C, [REDACTED] non-HDL-C, TC, [REDACTED] apoB, and hs-CRP; change from baseline in LDL-C; to Weeks 12 and 24, as appropriate), the ANCOVA assumption of normality will be assessed. If non-normality of the data is found at any time point for any parameter, either the data will be transformed so that it is normally distributed or a nonparametric test will be used instead of the planned ANCOVA.

Additional Post-randomization Adjunctive Triglyceride-lowering Therapy:

The number and percent of patients in each treatment group requiring additional (post-randomization) TG-lowering therapy will be summarized. The medications will be summarized by treatment group.

Safety Analyses

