4.2.2. Pharmacokinetics and Pharmacology

In both single- and multiple-dose studies, bempedoic acid is well absorbed (with a time to peak maximum concentration [C_{max}] of approximately <4 hours). The C_{max} of bempedoic acid and ESP15228 increased in proportion to increasing dose. The terminal elimination half-life ($t_{1/2}$) ranged from 15 to 27 hours for bempedoic acid and 20 to 33 hours for ESP15228.

[figure not shown]
In clinical drug-drug interaction studies, bempedoic acid 240 mg showed less than a 2-fold increase in the exposure of atorvastatin 10 mg, simvastatin 20 mg, pravastatin 40 mg, and rosuvastatin 10 mg in 2 statin drug-drug interaction studies (Studies 1002-007 and 1002-012). This increase was generally less pronounced when bempedoic acid 180 mg was administered with high dose statins (atorvastatin 80 mg, simvastatin 40 mg, pravastatin 80 mg, and rosuvastatin 40 mg) in Study 1002-037, suggesting that the combination is unlikely to alter safety profile of statins. No drug interaction occurred between daily bempedoic acid 180 mg and metformin in patients with type 2 diabetes mellitus (T2DM). A Phase 2 study evaluated and showed no effect of ezetimibe 10 mg on steady-state trough bempedoic acid plasma concentrations in 40 patients with hypercholesterolemia randomized to receive bempedoic acid plus ezetimibe (Study 1002-008). Results of a drug interaction study in 19 patients (16 evaluable for pharmacokinetics [PK]) with the oral contraceptive Ortho-Novum 1/35 in healthy women demonstrate no effect of daily bempedoic acid 180 mg on ethinyl estradiol or norethindrone exposure (Study 1002-017).

The results of the thorough QT/QTc (TQT) study (1002-022) showed no significant change in QTc. Following daily bempedoic acid 240 mg for 9 days, bempedoic acid does not prolong QT interval duration and has no clinically significant effect on heart rate and PR and QRS intervals.

[figure not shown]

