8.3.7. Treatment Week 12 (Visit T4; Day 85 ±3 days)

Patients will undergo the following assessments and procedures at Week 12 (Visit T4):

1. Concomitant medication review (ongoing)
2. Assess AEs, SAEs, and potential clinical endpoints (ongoing)
3. Weight
4. Vital signs
5. Central clinical laboratory evaluations:
 - Hematology, blood chemistry, and urinalysis
 - apoB
 - hs-CRP
 - HbA_{1C}
 - Basic fasting lipids (TC, calculated LDL-C, HDL-C, non-HDL-C, and TG)
 - PK Sample before dose

6. Diet and exercise counseling
7. Return of study drug; assessment and recording of dosing adherence
8. IWRS contact to obtain new MED ID numbers for double-blind study drug
9. Dispense double-blind study drug and provide dosing instruction

Note: If the patient discontinues at any scheduled visit after T1, or between study visits, please proceed to [Section 8.4.1](#) for detailed instructions.

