8.4. Early Withdrawal from Study or Treatment

Patients who withdraw from study drug prior to Week 24 (Visit T5) for any reason will be asked to continue to be followed for safety assessments, including basic fasting lipids, at clinic visit following the protocol-specified visit schedule (see [Section 8.3](#)).

Patients who temporarily withdraw from study drug prior to Week 24 (Visit T5) for any reason may restart study drug providing that 1) the patient and the investigator are in agreement regarding this course of action, 2) the patient has been off of study drug for 4 weeks or less; and 3) study drug can be started as soon as possible. For cases where the patient has been off of study drug for more than 4 weeks, the investigator must contact the medical monitor for approval prior to restarting study drug.

Patients who do not wish to continue to return to the clinic for safety assessments will be asked to participate in phone calls from the site at protocol-specified visits (see [Section 8.3](#)), or at a minimum at 24 weeks, to collect information on AEs, concomitant medications, and current health status.

The patient's decision to participate in the clinical study is voluntary. Patients may refuse to continue in the study and/or withdraw from participation in this study at any time, for any reason, specified or unspecified, and without penalty or loss of benefits to which the patient is otherwise entitled.

It is the right and duty of the Investigator to interrupt the treatment of any patient whose health or well-being may be threatened by continuation in this study. Such patients should be withdrawn from the study and should not be continued under a modified regimen.

Patients who are withdrawn from the study may not re-enter. The reasons for withdrawal from this study or treatment may include:

- Patient's withdrawal of consent
- Failure to comply with the protocol
- Lost to follow-up
- Illness, condition, or procedural complication (including AEs) affecting the patient's ability to participate or requiring prohibited medication
- The Sponsor or Investigator terminates the study
- In the Investigator's judgment, it is deemed in the best interest of the patient to discontinue his/her participation in the study
- Any other reason

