8.4.1. Procedures for Early Withdrawal

If a patient withdraws or is removed from the study for any reason, all "End of Study" procedures should be completed. Reason for withdrawal, date of the discontinuation, and date of the last dose of study drug should be recorded in the appropriate section of the eCRF.

Additionally, the discontinuation visit date must be registered in IWRS. Study drug assigned to the withdrawn patient may not be assigned to another patient.

All effort should be made to have each patient complete all study visits on schedule according to the protocol. Accommodations for early or late visits in special circumstances will be considered by the Sponsor to prevent early withdrawal. Written notice (regardless of cause) is to be provided within 48 hours of the withdrawal to the Sponsor personnel or the Medical Monitor. At the time of discontinuation, every effort should be made to ensure all relevant procedures and evaluations scheduled for the final study visit are performed.

Patients choosing to withdraw from the study early should be encouraged to return for all study scheduled clinic visits even if they are no longer taking IMP. Patients who withdraw from all aspects of the study will be asked to consent to clinical visits or phone calls for safety assessments, including AEs, concomitant medication, and current health status through Week 24 (Visit T5). Subjects who are unwilling to return for clinic visits should return for an end of study visit (Visit T5).

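### The schedule NOTE drops apoB and hs-CRP for off-drug patients who still attend Week 12, against Section 8.3.7, so apoB (and possibly hs-CRP) is imputed from placebo where it could have been measured

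*Protocol*

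**What the plan says.** **Collection.** For patients who have stopped study drug and still come to clinic, the NOTE in Protocol Section 8.3 (Table 2) and in Appendix 1 reads "Safety assessments should include clinical safety and basic lipid laboratories (except for apoB and hs-CRP"). Section 8.4 has the same focus: these patients are asked to "continue to be followed for safety assessments, including basic fasting lipids, at clinic visit". Basic fasting lipids are TC, LDL-C, HDL-C, non-HDL-C and TG, so they include neither marker.

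Three places say otherwise. Section 8.3.7 opens with "Patients will undergo the following assessments and procedures at Week 12 (Visit T4") and lists apoB and hs-CRP, with no exception for patients off drug. Footnote 3 to Table 2 says "All procedures will be completed for all patients at either EOS if completing the study or early withdrawal". Section 8.4.1 says that at discontinuation "every effort should be made to ensure all relevant procedures and evaluations scheduled for the final study visit are performed", and it encourages patients to "return for all study scheduled clinic visits even if they are no longer taking IMP".

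**Analysis.** SAP 7.5 tests Week 12 apoB at step 5 and Week 12 hs-CRP at step 6, each at two-sided 0.05. The analysis set is all randomized patients (SAP 5.2). Protocol 11.6 and SAP 18.2.1 apply the primary endpoint's multiple imputation to the step-down endpoints. In SAP Appendix 4, an off-drug bempedoic acid patient with a missing value (cohort 4) is imputed from placebo cohorts 5 and 7. SAP 18.2.1 analyses hs-CRP by Wilcoxon test with Hodges-Lehmann estimates, while Appendix 4 describes pooling over the 200 imputed datasets for ANCOVA only. The protocol synopsis still says of the secondary endpoints "Only observed case data will be included in each analysis (no imputation will be performed for missing data"); Protocol 11.1 lets the SAP prevail.

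**The concern.** For LDL-C, non-HDL-C and TC, an off-drug attender's own Week 12 value enters the all-randomized comparison. For apoB, at the same visit and often from the same blood draw, an assumed placebo-like value enters instead if the site has followed the NOTE. The imputation model uses only stratum and baseline, so it does not draw on the LDL-C and non-HDL-C measured that day. hs-CRP has no comparable proxy at all.

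The NOTE would also nearly empty the observed off-drug cohorts (7 and 8) for these two markers, leaving few data against which to check the assumption. What is at stake is the basis of two estimates in the confirmatory sequence, and consistent practice across sites that may read the conflicting passages differently.

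**Working it through.** **1. Which text a site would follow.** The NOTE is written for exactly the patients in question. Section 8.3.7 is a general visit list. Footnote 3 and the end-of-study procedures in Section 8.4.1 are tied to withdrawal or the final visit, not to a later Week 12 visit. Section 8.4.1's encouragement to keep attending does not say which assays are run. Following the NOTE is therefore reasonable, but the passages conflict.

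**2. Who is affected.** The plan has 300 patients at 2:1: 300 x 2/3 = 200 bempedoic acid and 100 placebo. SAP 18.1.3 treats a patient as off drug if the last dose is earlier than the Week 12 lab date minus 7. For a Day 85 draw that means a last dose on Days 1-77, at least 8 days before. No off-drug rate is given in the text available, so d = 5%, 10% and 15% are assumed: 200 x d = 10, 20 and 30 at most, if all attend and none restart. Patients who stop after Week 12 or restart before it are not affected. Those who do not attend lose LDL-C as well, so the NOTE does not change their position.

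**3. Could a withdrawal-visit sample fill the gap?** The Week 12 window is Days 72-127. With stop days spread evenly over Days 1-77 (assumption), a sample on the last-dose day falls in the window for 6/77 = 7.8% of stoppers, and one taken 7 days later for 13/77 = 16.9%. With no such visit it is 0%. That leaves 8.3-10, 16.6-20 or 24.9-30 patients without a value. A sample within 7 days of the last dose counts as on treatment under SAP 18.1.3, so even these would not be off-drug observations. The text of SAP 6.3 on early-termination data is not in the copy reviewed, so this step is only a rough guide.

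**4. Size for apoB.** Let r be the share of the on-drug effect that off-drug patients keep. The all-randomized effect, as a fraction of the on-drug effect, is (1 - d) + d x r. Placebo-based imputation sets r = 0. Dropping the imputation behaves like r = 1.

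| d | r = -1 | r = -0.5 | r = 0 (main analysis) | r = 0.1 | r = 0.25 | r = 1 (no imputation) |
|---|---|---|---|---|---|---|
| 5% | 0.90 | 0.925 | 0.95 | 0.955 | 0.9625 | 1.00 |
| 10% | 0.80 | 0.85 | 0.90 | 0.91 | 0.925 | 1.00 |
| 15% | 0.70 | 0.775 | 0.85 | 0.865 | 0.8875 | 1.00 |

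The shift from the main analysis is r x d: 0.5-1.5% of the on-drug effect at r = 0.1 and 1.25-3.75% at r = 0.25. A simulation of placebo-donor regression imputation (200 versus 100 patients, on-drug effect 0.75 SD, 300 trials, 50 imputations) agreed. At d = 5% and 10% it returned 0.94-0.95 and 0.90-0.91 whether the true r was -0.5, 0 or 0.5, while observed data returned 0.99-1.01.

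**5. Is r near 0 plausible?** Protocol 4.2.2 gives half-lives that "ranged from 15 to 27 hours for bempedoic acid and 20 to 33 hours for ESP15228". The fraction left after t hours is 2^(-t/half-life). At 8 days (192 h) and the longest half-lives, 2^(-192/27) = 0.7% of parent and 2^(-192/33) = 1.8% of metabolite remain. At 7 days (168 h) the figures are 1.3% and 2.9%. This is drug exposure, not lipid response, but it makes placebo-like values plausible.

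**6. How much worse than placebo would matter?** Assume an on-drug effect of 0.5 SD. The standard error is sqrt(1/100 + 1/200) = 0.1225 SD, so the critical difference is 1.96 x 0.1225 = 0.24 SD. Significance is lost if off-drug patients are (0.5 x (1 - d) - 0.24)/d SD worse than placebo: 4.7 SD at 5%, 2.1 SD at 10% and 1.2 SD at 15%.

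**7. A knock-on in Appendix 4.** Newly measured off-drug bempedoic acid values would fall in cohort 8. Appendix 4 uses cohort 8 as donors for cohort 2, who are on treatment, whereas SAP 18.1.3 likens those patients to others still on treatment. Assume cohort 2 has 4 of 200 patients and cohort 8 has 10, 20 or 30 placebo-like ones. The cohort 8 share of donors is then 10/196, 20/196 or 30/196 = 5.1%, 10.2% or 15.3%. The overall effect moves by 4/200 x share = 0.10%, 0.20% or 0.31% of the on-drug effect. That is a matter of coherence, not a material bias.

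**The case against.** The strongest reply is that the plan already handles this. SAP 18.1.3 gives a reasoned assumption, the half-lives support it, and it tends toward no difference. The completer, on-treatment and observed-data analyses (SAP 18.2.3) repeat the apoB and hs-CRP comparisons without imputation, in effect under missing-at-random. A reader might infer from the NOTE that no sensitivity analysis varies the placebo-like assumption. The documents do not support that: main and no-imputation analyses together run from about r = 0 to r = 1. What remains is narrower. All of these analyses leave out patients with missing values, and none tests off-drug values worse than placebo.

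A reader might also infer that steps 5 and 6 depend equally on the imputation. Only apoB is clear. For hs-CRP, Protocol 11.6 and SAP 18.2.1 point to imputation, but without a pooling rule for the Wilcoxon/Hodges-Lehmann result its role at step 6 is not settled.

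Finally, Section 8.4.1 can be read more broadly. The visit notes in Sections 8.3.5 to 8.3.7 send anyone who discontinues there, and it mentions patients no longer on drug. That is fair, and it is why this is in part an internal conflict to be reconciled. It does not secure a Week 12 sample, because the end-of-study panel it asks for belongs to the time of discontinuation.

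**Conclusion.** The point holds as a cheap improvement to collection, with a small expected effect. The NOTE conflicts with Section 8.3.7, footnote 3 and Section 8.4.1, and a site following it replaces a measurable apoB value by a placebo-based one in at most 10, 20 or 30 of 200 bempedoic acid patients (5%, 10% or 15% off drug, assumed). The likely shift in the apoB estimate is about 0.5-1.5% of the on-drug effect at r = 0.1; a shift of 5-15% would need full retention of effect off drug.

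It would go too far to read this as biased results or a loss of error control. No bias is shown, the imputation pulls toward no difference unless off-drug patients do worse than placebo, and the primary endpoint, steps 2-4 and Type I error control are unaffected. The hs-CRP pooling rule and the synopsis sentence are secondary points of completeness and alignment.

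**What to change.** 1. Delete the parenthesis that excepts apoB and hs-CRP from the NOTE in Table 2 and Appendix 1, so that both are assayed at the scheduled Week 12 draw in every attending patient. Reconcile the NOTE with Section 8.3.7, footnote 3 and Section 8.4.1. Cost: a wording amendment, two assays and possibly one extra tube for a few patients, with no extra visit. Tube requirements are in a laboratory manual not available here.
2. In SAP Appendix 4, remove cohort 8 from the donor row for cohort 2 and from the code for cohorts 1-3, to match SAP 18.1.3. Cost: one table row and one line of code.
3. Secondary: state how the hs-CRP Wilcoxon/Hodges-Lehmann results are combined over the 200 imputations, and align the synopsis sentence on no imputation with Protocol 11.6 and the SAP.
4. The SAP addendum reports the planned analysis as completed, so collection is probably over. In that case, report by arm the number of off-drug patients without Week 12 apoB and hs-CRP. Their same-visit LDL-C and non-HDL-C, compared with placebo, would give an indirect check for apoB. Add one delta-adjusted sensitivity analysis, labelled post hoc, that includes values worse than placebo: for apoB, shift cohort 4 over r = -1 to r = 1; for hs-CRP, use a ratio scale. Cost: a count and one additional analysis.
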